PROTOCOL

Title: A Pilot Study: A Comparison of Liposomal Bupivacaine (“Exparel™”) to Bupivacaine HCl in Transversus Abdominis Planus (“TAP”) Block for Abdominal Gynecologic Surgery

Sponsor: [name],
Abington Memorial Hospital, [name]
Hanjani Institute for Gynecologic Oncology
[contact]

Principal Investigator: [name]
Abington Memorial Hospital
[name]
[contact]
[contact]

The following persons are sub-investigators for this research study:

[name]
[name]
[name]
[name]
[name]

I. Objectives/Purpose

The proposed pilot study is evaluating the use of Exparel™ in an anesthesia protocol for patients undergoing major lower abdominal gynecologic surgery. Exparel™ is a formulation of liposomal bupivacaine that is reputed to have a much longer duration of action compared to bupivacaine. Exparel™ has been originally demonstrated to be safe and effective in bunionectomy and hemorrhoidectomy. It has recently gained FDA approval for all surgical site infiltration including TAP (Transversus Abdominis Planus block) blocks. Exparel™ has also been studied in other procedures and demonstrated reduction in opioid use and median length of stay (LOS).

Currently, patients on the gynecologic oncology service undergoing major abdominal surgery are receiving a type of regional anesthesia using bupivacaine HCl known as a TAP block as part of an effort to decrease narcotic use post-operatively and decrease hospital length of stay. Bupivacaine has a known eight to twelve hour duration of action, thus addressing immediate post operative pain. As Exparel™ is anticipated to have a longer duration of action, the purpose of this study is to determine if TAP blocks with Exparel™ have an advantage over standard TAP blocks with bupivacaine HCl in reducing length of hospital stay in a randomized controlled trial. Our hypothesis is that TAP blocks with Exparel™ will result in reduced length of stay contributing to significant hospital cost savings. Secondary outcomes include total narcotic use (hypothesized to be reduced) and overall complication rates (hypothesized to remain unchanged). Given there are no published data on the efficacy and safety of using Exparel™ in open gynecologic abdominal surgery, this will be a pilot study.

II. Background Information:

Overview of Clinical Studies

Comparative efficacy and safety of liposome bupivacaine versus bupivacaine HCl has been analysed in order to reduce opioid burden in the post surgical setting. Specific procedures such as inguinal hernia repair, total knee arthroplasty, hemorrhoidectomy, breast augmentation, or bunionectomy, have been included in recent studies. In one of the pooled analysis, liposomal bupivacaine has been shown to reduce pain scores at a statistically significant level. Patients receiving liposomal bupivacaine were also less likely to experience opioid related adverse events.

The following safety information is derived from Exparel™'s website including prescribing information and important safety information. Exparel™ is indicated for single-dose administration into the surgical site to produce post surgical analgesia. In clinical trials, the most common adverse reactions following Exparel™ administration were nausea, constipation and vomiting. Other common adverse reactions include pyrexia, dizziness, anemia, hypotension, prurities (incidence between 2% and 10%). The rare adverse reactions (incidence less than 2%) include, but are not limited to, chills, erythema, bradycardia, pain, edema, syncope.

Exparel™ has been demonstrated to be safe and effective for procedures such as hemorrhoidectomy and bunionectomy, as well as for surgical site infiltration such as TAP blocks. Exparel™ use in open abdominal gynecologic surgery for TAP block has not yet been studied specifically. Monitoring of cardiovascular and neurological status, as well as vital signs, should be performed before, during and after administration of Exparel.

III. Procedures

Patients undergoing laparotomy will be randomized to either Exparel™ or bupivacaine HCl. Randomization will occur through computer generated random assignment. Given the nature of the medication itself, bupivacaine and Exparel™ have physical inherent differences after manufacture and the anesthesiologist will not be able to be blinded. Patients will be blinded to the type of TAP block they receive.

A. Inclusion and Exclusion of Subjects

Inclusion criteria

1. TAP blocks placed after the laparotomy incision is closed, but before the patient is awake, and placed under ultrasound guidance with correct identification of the correct abdominal plane.
2. Consent for TAP block signed by patients preoperatively by anesthesiology

Exclusion criteria

1. All pregnant patients
2. All patients under 18 years of age
3. minimally invasive surgery such as laparoscopy or robotic assisted laparoscopy
4. medical contraindications to use of bupivacaine or liposomal bupivacaine such as severe hepatic and/or renal disease

We hope to include 128 subjects in this study in order to reach statistical significance. Please see Appendix 1 for sample size calculations.

B. Assessment of Efficacy/Measurement

Efficacy will be measured through comparing length of hospital stay, total narcotic use, and complications/adverse effects such as nausea, vomiting, constipation and pruritis.

C. Treatment of Subjects

Subjects will need to provide consent for both the surgery and TAP block provided by an anesthesiologist. Post operatively, narcotic availability will not be withheld.

D. Validity

Internal validity will be addressed by randomizing the subjects to avoid selection bias. Patients will also be blinded to the type of TAP block they will receive to eliminate recall bias.

E. Discontinuation of the Study

Study involvement will be discontinued if the subject displays an immediate reaction to the local anesthetic, whether bupivacaine or liposomal bupivacaine. Interim analysis after enrollment of first 50 patients will be done and if there is a clear benefit of use of Exparel™ over Bupivacaine, the study will be discontinued.

IV. Methods

1. Informed consent will be offered to patients in pre op area and patients will be randomized. Charts will be labeled with a card stating bupivacaine, vs Exparel. A consent for anesthesia including TAP block is signed by patients preoperatively.
2. All TAPs will be placed after the laparotomy incision is closed but before the patient is awake.
3. Anesthesia will place the TAP with Ultrasound.
4. We will typically not open the Exparel before closure of fascia. Once EXPAREL is open it is only good for 4 hours so should NOT be opened until right before you are ready to use
5. Surgeon will notify anesthesia if the incision is extended above the umbilicus
6. When performing a bilateral TAP with Exparel and the incision is below the umbilicus: the 20 ml vial of Exparel, containing 266 mg, will be diluted with 20 ml of 0.25% bupivacaine (containing 50 mg of bupivacaine) and 20 ml saline (60 ml total). That total volume will be divided into two 30 ml syringes, and each will be used (per side) for the TAP blocks.

Every anesthesiologist that will be administering the TAP block in this study will perform the TAP block in a controlled fashion under certain guidelines whether using bupivacaine or Exparel™. Every surgeon that is participating as a sub-investigator will be informed of the correct procedure and protocol.

VII. Ethics

There has been much data showing that TAP block is successful and reduces post operative pain using bupivacaine. The unknown effect of Exparel™ in TAP block for gynecologic surgery, especially in exploratory laparotomy, is the reason for the study. Exparel™ is much more costly than bupivacaine. If the use of Exparel™ results in significant reduction in length of stay, then expenditure for this agent is justifiable. Given that Exparel™ has been used in other types of surgeries for post operative pain relief, it is ethical to use Exparel™ in this type of study. Exparel™'s adverse effect profile, which includes nausea, vomiting and pruritis, is acceptable and therefore ethical to use in this study.

VIII. Data handling and Record keeping

- 1) review of charts - resident and attending notes
- 2) review of medication administration
- 3) two independent reviewers of charts

IX. Project Timetable/Flowchart

- 1) February 2016- IRB Submission - Consent/Protocol

- 2) March 2016 - IRB Resubmission
- 3) June 2016 - IRB Resubmission
- 3) July 2017 - February 2017 data gathering (8 months)
- 4) March 2017 - data analysis

References

- Baxter Richard, Bramlett Kenneth, Onel Erol, Daniels Stephen. Impact of Local Administration of liposome bupivacaine for post surgical analgesia on wound healing: a review of data from ten prospective, controlled clinical trials. *Clinical Therapeutics* 2013. 35 (3): 312-20.
- Bergese Sergio D, Ramamoorthy Sonia, Patou Gary, Bramlett Kenneth et al. Efficacy profile of liposomal bupivacaine, a novel formulation of bupivacaine for post surgical analgesia. *Journal of Pain Research* 2012;5 107-116
- Dasta Joseph, Ramamoorthy Sonia, Patou Gary, Sinatra Raymond. Bupivacaine liposome injectable suspension compared with bupivacaine HCl for the reduction of opioid burden in the post surgical setting. *Current Medical Research & Opinion* 2012. 28 (10): 1609-15.

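### The adverse-effect comparison draws on physician notes and medication records, with no nursing source, no event definitions and no stated masking of note-writers or reviewers, so events may be under-recorded and may be recorded differently by arm

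*Protocol*

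**What the plan says.** Section I of the protocol makes complications a secondary outcome and states the expectation: "overall complication rates (hypothesized to remain unchanged". Section III.B lists among the measures "complications/adverse effects such as nausea, vomiting, constipation and pruritis", and section IV item 11 repeats complications and adverse effects as a collection goal.

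Section VIII is the only description of where data come from. It has three entries: "review of charts - resident and attending notes", "review of medication administration" and "two independent reviewers of charts". No entry is assigned to a particular outcome. Neither document gives a definition, time window, scheduled assessment, nursing source, patient report or collection form for any of the four symptoms. The SAP covers sample size and randomization only.

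On blinding, section III says "the anesthesiologist will not be able to be blinded" and "Patients will be blinded to the type of TAP block they receive". Nothing is said about residents, attendings, surgeons or the chart reviewers. Section IV item 1 adds "Charts will be labeled with a card stating bupivacaine, vs Exparel". Items 7 and 9 of section IV have the surgeon infiltrate study drug when the incision extends above the umbilicus, in a different volume in each arm.

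**The concern.** The four named effects are symptoms experienced at the bedside. Whether a given episode reaches a resident or attending note depends on someone reporting it and a physician choosing to write it down. A second reader of the same notes reduces abstraction error but cannot recover an episode that was never entered. The medication record could fill part of the gap through as-needed treatment, but the plan does not say that it will be used for this.

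Two consequences follow. If episodes are missed equally in both arms, the absolute difference shrinks, and the result drifts toward the one the protocol expects. A reader could then take a failure of measurement as confirmation that complication rates are unchanged. If episodes are missed unequally because those writing or abstracting know the arm, a difference can appear where none exists. The chart card makes such knowledge likely, although the protocol does not state it.

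**Working it through.** The plan states no adverse-effect rate, capture fraction or power, so there is no figure of its own to reproduce. The check has a textual part and an illustration.

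**Text, side by side.**
- III.B names four symptoms as measures. VIII names two record types and assigns neither to them. No rule therefore says what counts as an event.
- VIII lists two independent reviewers. Section III blinds the patient and says the anesthesiologist cannot be blinded. The reviewers and note-writers are not mentioned, and IV item 1 labels the chart with the drug. Their knowledge of the arm is likely but not stated.

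**Illustration: inputs.**
- n = 64 per arm, from the SAP. That number was set for a 0.5-day difference in length of stay, not for adverse effects.
- Two-sided 5% test (assumed; the documents state no alpha).
- True event rates and capture fractions (assumed throughout).

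**Formulas.** Recorded rate = true rate × capture fraction. The test is the pooled two-proportion z test, z = (x₁/n − x₂/n) / √[2p̄(1 − p̄)/n], with p̄ = (x₁ + x₂)/(2n). The rejection probability is the sum of the binomial probabilities over all pairs (x₁, x₂) with |z| > 1.96.

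**(a) Equal under-recording, true rates 50% vs 25%.**

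| Capture, both arms | Recorded rates | Difference | Power |
|---|---|---|---|
| 100% | 50.0% vs 25.0% | 25.0 points | 0.849 |
| 70% | 35.0% vs 17.5% | 17.5 points | 0.626 |
| 50% | 25.0% vs 12.5% | 12.5 points | 0.439 |

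The ratio of rates stays at 2 in every row. What is lost is the absolute difference and the power.

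Other assumed true rates show the same pattern. For 40% vs 20%, by the normal approximation, power is 70% at full capture, 56% at 80%, 42% at 60% and 35% at 50%. For 30% vs 20%, by enumeration, it is 26% at full capture and 17% at 70%.

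**(b) Unequal recording, true rate 40% in both arms.**

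| Capture, control vs Exparel | Recorded rates | Rejection |
|---|---|---|
| 60% vs 60% | 24% vs 24% | 0.050 |
| 60% vs 50% | 24% vs 20% | 0.083 |
| 80% vs 70% | 32% vs 28% | 0.080 |
| 60% vs 40% | 24% vs 16% | 0.200 |

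In the last row 0.199 of the 0.200 falls in the direction favouring Exparel. That direction is built into the assumption; reversing the capture fractions would reverse it. With capture of 80% in one arm and 60% in the other, and true rates from 20% to 50%, the spurious gap is 4 to 10 points (20% × 0.20 to 50% × 0.20). The chance of a significant result in that direction is then about 10% to 22% (normal approximation).

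**The case against.** Several points on the other side have force.

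- **Physician notes are not the sole source.** A reader might infer from VIII that adverse effects come from notes alone. They do not: medication administration is also reviewed, and antiemetic, antipruritic and laxative doses would appear there. This stands. What remains is that the plan does not say the record serves that purpose.
- **The note-writers are not stated to be unblinded.** A reader might infer that an unblinded team writes the notes. The protocol says this only of the anesthesiologist. The chart card and the surgeon's infiltration make knowledge of the arm likely, but that is an inference.
- **Under-counting is not shown.** The documents give no event rate and no capture fraction. Only a risk can be claimed.
- **The outcome is wider than four symptoms.** The secondary outcome is the overall complication rate, and III.B gives the four as examples. Physician notes are a reasonable source for other surgical and medical complications, and this point does not question them there.
- **The illustration depends on its inputs.** A halving from 50% to 25% is a large effect for an outcome expected not to change. At 30% vs 20% the trial has only 26% power even with complete capture, so sample size is the main limit and better sources would not cure it. A 10-point capture gap raises false rejection only from about 5% to about 8%.
- **A common rule does not make recording blind.** Nursing entries and as-needed doses may come from staff who can see the same card. The fix therefore has to address the card and concede what it cannot remove.

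**Conclusion.** The concern holds in a limited form. The plan names physician notes and medication administration as its only sources, ties neither to the four named effects, lists no nursing record, and does not state whether note-writers or reviewers are blinded although charts carry a drug card. These symptoms may be under-recorded, which favours a finding of no change, and recording may differ by arm.

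The size is unknown. With every rate and capture fraction assumed, 64 per arm and a two-sided 5% test, the loss is 22 points of power at 70% capture (85% to 63%) and 41 points at 50% capture (85% to 44%) for 50% vs 25%. False rejection with no true difference is about 8% for a 10-point capture gap and 20% for a 20-point gap, at a 40% true rate.

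The documents do not support saying that events are in fact under-counted, or that a bias toward Exparel exists. The weight is moderate: a named secondary outcome in a pilot is exposed, length of stay is not, and the repair is cheap enough that it should be made.

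**What to change.** Amend section VIII in four respects.

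1. Add nursing notes and flowsheets as a source for nausea, vomiting, constipation and pruritus. Keep physician notes as a source for these and for other surgical and medical complications.
2. Define each named effect by one rule applied identically in both arms: a nursing or physician entry, or an as-needed dose of the matching class (antiemetic, antipruritic or laxative) in the medication record already being reviewed.
3. Keep the drug card out of the records given to the two reviewers, so that they abstract adverse effects without knowing the arm as far as possible. Masking may be incomplete, because other parts of the record may name the study drug.
4. State that recording by ward staff may still not be blind, so that the comparison is read with that limit.

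The cost is one protocol paragraph, some extra abstraction time for the same two reviewers, and the work of preparing records without the card. Recorded rates will be higher than from physician notes alone. As-needed doses are an imperfect proxy, since some will be given without the symptom and some symptoms will go untreated. No treatment changes.

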STATISTICAL ANALYSIS PLAN

Title: A Pilot Study: A Comparison of Liposomal Bupivacaine (“Exparel™”) to Bupivacaine HCl in Transversus Abdominis Planus (“TAP”) Block for Abdominal Gynecologic Surgery

Sponsor: [name],
Abington Memorial Hospital, [name]
Hanjani Institute for Gynecologic Oncology
[contact]

Principal Investigator: [name]
Abington Memorial Hospital
[name]
[contact]
[contact]

Statistical analysis was performed by the department statistician in order to calculate the sample size necessary to achieve a statistically significant decrease by 0.5 days in length of stay based on the department’s average length of stay for open abdominal surgery (3 days). N was calculated to be 128, 64 in each arm. Microsoft Excel program was then used to create a randomization for either control or intervention for a total of 150 patients to anticipate 15% dropout rate.
